APPENDIX L – SCD/CRRT BLOOD PRIMING PROTOCOL

Prismaflex HF1000

The blood volume for the Prismaflex HF1000 is 165 ml and for the SCD is 120 ml, leading to a total extracorporeal circuit volume (ECV) is 285 ml. Blood prime will occur if the ECV total is greater than 10% of the patient's blood volume, based on an estimate of blood volume = 70 ml/kg x patient body weight (kg) [24]. As such, there are three patient weight ranges that will dictate the need, or lack thereof for blood priming:

Patient weight (kg)	Total Blood Volume	Blood Prime Need: HF1000
>40 kg	>2800 ml	None (a)
24-40 kg	1680-2800 ml	HF1000 alone (b)
15-24 kg	1050-1680 ml	HF1000+SCD (c)

This additional circuit blood volume for the standard SCD in 24-40 kg patients can be handled with blood priming with matched blood similar to the standard practice in neonates. The situation is most commonly encountered in neonatal CRRT, where circuit ECV can represent nearly 50% of patient blood volume, yet the same principles apply for this clinical study. [25]

Renaflo HF 400, HF 700, and HF 1200

The following tables display the same breakdown of blood prime need by weight for the extracorporeal blood volume of the Renaflo HF 400, HF 700, and HF 1200.

Renaflow HF 400

Renaflo HF 400 ECV 28ml + Braun Tubing ECV 156ml + SCD ECV 120ml = 304ml Total ECV

Patient Weight (kg)	Total Blood Volume	Blood Prime Need: HF 400
>43 kg	>3010 ml	None (a)
26 – 43 kg	1820 – 3010 ml	HF400 alone (b)
15 – 26 kg	1050 – 1820 ml	HF400 + SCD (c)

Renaflow HF 700

Renaflow HF 700 ECV 53ml + Braun Tubing ECV 156ml + SCD ECV 120ml = 329ml Total ECV

Patient Weight (kg)	Total Blood Volume	Blood Prime Need: HF 700
>47 kg	>3290 ml	None (a)
30 – 50 kg	2100 – 3290 ml	HF700 alone (b)
15 – 30 kg	1050 – 2100 ml	HF700 + SCD (c)

Renaflow HF 1200

Renaflow HF1200 ECV 83ml + Braun Tubing ECV 156ml + SCD ECV 120ml = 359ml Total ECV

Patient Weight (kg)	Total Blood Volume	Blood Prime Need: HF 1200
>51 kg	>3570 ml	None (a)
34 – 51 kg	2380 – 3570 ml	HF1200 alone (b)
15 – 34 kg	1050 – 2380 ml	HF1200 + SCD (c)

Investigators should use the reference letters in the third column (i.e. a, b, or c) to determine the blood prime protocol in the text below.

- a) For patients >40 kg: The blood volume for this patient population is >2800 ml, so the HF1000 plus the SCD represents <10% of the patient blood volume. Thus, for patients >40 kg:
 - i. The initial and all new CRRT circuits will be not primed with blood but with crystalloid or other fluid that is the local standard of care.
 - ii. For daily SCD filter changes (not associated with a CRRT circuit change), a new crystalloid primed SCD will be placed in line with the CRRT circuit without need for blood priming.
 - iii. The investigator can prime with blood or other colloid if they believe it is clinically indicated.
- b) For patients >24-40 kg: The blood volume for this patient population is >1680-2800 ml, thus the SCD alone represents <10% of the patient blood volume, but the ECV of the SCD and any CRRT circuit will comprise >10% of the total patient blood volume. Thus, for patients >24 kg:
 - i. The initial and all new CRRT circuits will be primed with blood per the local standard of care protocol.
 - ii. For initial and daily SCD filter changes (not associated with a CRRT circuit change), a new crystalloid primed SCD will be placed in line with the CRRT circuit without need for blood priming.

- iii. The investigator can prime the SCD with blood or other colloid if they believe it is clinically indicated.
- c) For patients 15-24 kg: The blood volume for this population is <1680 ml, thus the HF1000 + SCD ECV represents >10% for the entire range of patient weight from 15-24 kg. Thus, for patients with a weight of 15-24 kg:
 - i. A crystalloid primed SCD circuit will be placed in line with a crystalloid primed CRRT circuit. For the initial CRRT/SCD circuit, the entire CRRT + SCD circuit will then be primed with blood per local standard of care prior to initiating CRRT /SCD therapy with the patient. Given the relatively large blood ECV to patient size in this group, the following patient lab parameters should be achieved prior to initiating CRRT/SCD therapy to prevent severe acidosis or hypocalcemia
 - a. Patient pH of at least 7.20
 - b. Patient ionized calcium of at least 1.1 mmol/L
 - ii. Patient should be given calcium gluconate IV (at least 300 mg) at the start of CRRT/SCD therapy.
 - a. An equivalent about of IV calcium can be given in a different formulation (ex. 100 mg of IV calcium chloride).
 - iii. Once the CRRT+SCD therapy is initiated, patient ionized calcium and pH should be obtained no later than 15 minutes after achievement of final CRRT blood flow and effluent rates.
 - iv. For the daily SCD circuit change, one of two options will be available:
 - a. A completely new CRRT circuit can be used with the SCD circuit with a repeat of the procedure in the paragraph above
 - b. A circuit to circuit prime can be performed per local standard of care whereby the blood in the previous CRRT + SCD circuit is used to prime a new CRRT + SCD circuit

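### Appendix L: the HF 700 row b upper weight should be 47 kg, not 50 kg, and priming texts a to c carry HF1000 weights that conflict with the other filters' tables

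*Combined protocol and SAP*

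**What the plan says.** Section 6.2.2 requires a blood prime when the total extracorporeal volume exceeds 10% of blood volume, taken as 70 ml/kg, and refers to Appendix L for the trial's minimum priming standards. Appendix E approves four hemofilters: HF1000, HF 400, HF 700 and HF 1200.

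Appendix L gives one table per filter. Row a means no blood prime, row b a prime of the CRRT circuit only, and row c a prime of the CRRT circuit plus the SCD. For HF 700, row a is above 47 kg (above 3290 ml) and row b is 30–50 kg (2100–3290 ml). After the tables comes the selector: "Investigators should use the reference letters in the third column".

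The texts then state weights of their own:
- Text a: "For patients >40 kg: The blood volume for this patient population is >2800 ml", with the reason "so the HF1000 plus the SCD represents <10% of the patient blood volume". Its first instruction is "The initial and all new CRRT circuits will be not primed with blood".
- Text b: "For patients >24-40 kg: The blood volume for this patient population is >1680-2800 ml". Its reasoning is not tied to one filter ("but the ECV of the SCD and any CRRT circuit will comprise >10"%), and its instructions are introduced by "Thus, for patients >24 kg".
- Text c: "Thus, for patients with a weight of 15-24 kg". It adds a blood prime of the SCD, pH and ionized calcium thresholds before starting, intravenous calcium, and a check within 15 minutes.

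**The concern.** In HF 700 row b, the weight and the volume describe different patients, and the weight overlaps row a. The selector cannot resolve this, because a child above 47 and up to 50 kg has two letters with opposite instructions.

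The weights in texts a to c are the HF1000 cut-offs (24 and 40 kg), yet the same texts serve filters with cut-offs of 26/43, 30/47 and 34/51 kg. Text b also drops its upper limit between heading and instruction. By printed weight alone, a child above 40 kg meets both text a (do not prime) and text b (prime).

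The stake is bedside safety in critically ill children. Section 6.2.2 says blood priming can itself cause hypotension, so an unneeded prime carries some risk. In the other direction, a site acting on the text weights could leave a circuit above 10% unprimed, or omit the text c precautions in a smaller child.

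**Working it through.** **Inputs**, all from Appendix L: blood volume 70 ml/kg; prime if the extracorporeal volume exceeds 10% of it, i.e. 7 ml per kg; SCD 120 ml; Braun tubing 156 ml; filter volumes as printed.

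**Reproducing the printed cut-offs.** Upper cut = total volume/7. Lower cut = CRRT circuit without the SCD/7.

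| Filter | CRRT circuit (ml) | With SCD (ml) | Upper cut (kg) | Printed | Lower cut (kg) | Printed |
|---|---|---|---|---|---|---|
| HF1000 | 165 | 285 | 40.7 | 40 | 23.6 | 24 |
| HF 400 | 28 + 156 = 184 | 304 | 43.4 | 43 | 26.3 | 26 |
| HF 700 | 53 + 156 = 209 | 329 | 47.0 | 47 (row a), **50 (row b)** | 29.9 | 30 |
| HF 1200 | 83 + 156 = 239 | 359 | 51.3 | 51 | 34.1 | 34 |

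Every printed cut-off is within 1 kg of the rule except the 50, which is 3 kg too high. It is also the only weight bound in the four tables that does not reproduce its own volume: 50 × 70 = 3500 ml, not 3290 ml, whereas 47 × 70 = 3290 ml.

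**HF 700 at 48–50 kg.** Share = 329/(70 × kg); margin = 329 − 7 × kg.
- 48 kg: 329/3360 = 9.8%; 329 − 336 = −7 ml.
- 50 kg: 329/3500 = 9.4%; 329 − 350 = −21 ml.

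The circuit is below the limit, so row a is right. Row b would add a blood prime of the 209 ml CRRT circuit.

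**Table letter b, but text a's weight (above 40 kg).** Whole circuit left unprimed if the weight is followed:
- HF 400: 41 kg, 304/2870 = 10.6% (17 ml over); 43 kg, 304/3010 = 10.1% (3 ml over).
- HF 700: 41 kg, 329/2870 = 11.5% (42 ml over); 47 kg, 329/3290 = 10.0% (0 ml).
- HF 1200: 41 kg, 359/2870 = 12.5% (72 ml over); 45 kg, 359/3150 = 11.4% (44 ml over); 51 kg, 359/3570 = 10.1% (2 ml over).

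**Table letter c, but text b's weight (above 24 kg).** This covers HF 400 at 24–26 kg, HF 700 at 24–30 kg and HF 1200 at 24–34 kg. For example, at 28 kg on HF 700 the CRRT circuit alone is 209/1960 = 10.7%, so the table gives c. Following text b still blood-primes the CRRT circuit. The crystalloid-primed SCD alone is 120/1680 = 7.1% at 24 kg, falling to 120/2380 = 5.0% at 34 kg. What is lost is the SCD blood prime and the text c pH and calcium steps.

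**The case against.** The 50 is an evident slip that the cells around it correct. It errs only towards extra priming, in about 3 kg on one of four filters. Text a lets the investigator prime anyway, so priming at 48–50 kg breaches no limit. Section 6.2.2 adds that the bradykinin reaction is usually linked to a membrane not used in this study, and that centers have their own mitigation.

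The text weights are correct for the HF1000, and texts a and c name that filter. A site would have to ignore the selector to be misled. Text b's statement about any CRRT circuit is true for its headed range: the smallest case is 285/2800 = 10.2%. Its heading also supplies the missing upper limit. Circuit calcium is checked at least hourly at initiation (section 6.2.1), and the optional Appendix K checks patient ionized calcium before and 5 minutes after starting. The hypotension rescue in section 6.2.2 covers a fall in pressure.

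Most of this stands, and it keeps the point minor. It does not remove it. A reader of the HF 700 table by weight gets two letters, and row b turns a discretionary prime into an instruction. At 48–50 kg it leads to a text whose premise, more than 10%, is false there. For the text weights the objection largely succeeds: they mislead only a site that does not follow the letter. Even so, the hourly checks are of circuit calcium, and the Appendix K calcium checks do not replace text c's pH threshold.

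**Conclusion.** The concern holds and is minor. HF 700 row b is wrong as written: its upper weight should be 47 kg, and as printed it calls for an unneeded 209 ml blood prime at 48–50 kg, where the circuit is 7–21 ml under the limit. The weights in texts a to c are a conditional hazard: up to 72 ml over the limit at 41 kg on HF 1200, but only if a site acts on the text weight instead of the table letter. All figures rest on the protocol's own 70 ml/kg, 10% rule and circuit volumes. How many of the up to 30 children would fall in these weight bands is unknown, because the protocol gives no distribution of weight or filter. Sample size, endpoints and analyses are untouched.

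**What to change.** In the HF 700 table, change row b from 30–50 to 30–47 kg. Delete the weights and volumes from texts a, b and c, or label them as HF1000 only and end text b's instruction line at 40 kg. State that the letter in the filter's own table alone decides. Send sites a notice.

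The cost is a wording correction in Appendix L with the IRB approval that section 12 expects for protocol changes, at up to 10 centers. Design, sample size and data collection do not change.

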APPENDIX M – PLACEMENT OF SCD IN CRRT / ECMO CIRCUIT
